9.5 Serious Adverse Event

An SAE is any untoward medical occurrence that at any dose:

- Results in death.
- Is life-threatening. NOTE: The term "life-threatening" in this definition refers to an event in which the subject is at risk of death at the time of the event; it does not refer to an event that hypothetically might cause death if it were more severe.
- Requires inpatient hospitalization or prolongation of existing hospitalization.
- Results in persistent or significant disability/incapacity.
- Is a congenital anomaly/birth defect.
- Is otherwise considered as medically important.

Important medical events that may not result in death, be life-threatening, or require hospitalization may be considered as SAEs when, based upon appropriate medical judgment, they may jeopardize the subject or may require medical or surgical intervention to prevent one of the outcomes listed in this definition. Examples of such events include allergic bronchospasm requiring intensive treatment in an emergency room or at home, blood dyscrasias or convulsions that do not result in subject hospitalization, or the development of drug dependency or drug abuse.

For the purposes of reporting, any suspected transmission of an infectious agent via an IP is also considered a serious adverse reaction and all such cases should be reported in an expedited manner.

9.6 Events that Do Not Meet the Definition of an SAE

Elective hospitalizations to administer, or to simplify trial treatment or trial procedures (e.g. an overnight stay to facilitate chemotherapy and related hydration therapy application) are not considered as SAEs. However, all events leading to unplanned hospitalizations or unplanned prolongation of an elective hospitalization (e.g., undesirable effects of any administered treatment) must be documented and reported as SAEs.

9.7 Events Not to Be Considered as AEs/SAEs

Medical conditions are present at the initial trial visit that do not worsen in severity or frequency during the trial are defined as Baseline Medical Conditions, and are NOT to be considered AEs. Progression of underlying disease is not an AE and therefore not an SAE per se, rather an efficacy end-point, unless deemed to be causally related to administration of IPs. However, if adverse signs or symptoms occur in association with disease progression then these should be recorded as AEs and reported as SAEs if meeting any seriousness criteria.

9.8 Methods of Recording and Assessing Adverse Events

At each trial visit, the subject will be queried on changes in his/her condition. During the reporting period of the trial any unfavorable changes in the subject's condition will be recorded as AEs, whether reported by the subject or observed by the Investigator.

Complete, accurate and consistent data on all AEs experienced for the duration of the reporting period (defined below) will be reported on an ongoing basis in the appropriate section of the eCRF. Among these AEs, all serious AEs must be additionally documented and reported using the appropriate section of the eCRF. It is important that each AE report include a description of the

event, its duration (onset and resolution dates (/times "/times" to be completed when it is important to assess the time of AE onset relative to the recorded treatment administration time)), its severity, its relationship with the trial treatment, any other potential causal factors, any treatment given or other action taken (including dose modification or discontinuation of the IPs) and its outcome. In addition, serious cases should be identified and the appropriate seriousness criteria documented. Specific guidance can be found in the eCRF completion and monitoring conventions provided by the Sponsor.

9.9 Adverse Event Reporting Period

The adverse event reporting period for safety surveillance begins when the subject is included into the trial (date of first signature of informed consent) and continues through the trial's posttreatment follow-up period, defined as 30 days from the final administration of the trial treatment or immediately before initiation of any other anticancer therapy, whichever comes first.

9.11 Safety Reporting to Health Authorities, Institutional Review Boards and Investigators

The Sponsor will send appropriate safety notifications to Health Authorities in accordance with Spanish clinical regulation via Eudravigilance within the timelines specified in GCP. The Investigator must comply with any applicable site-specific requirements related to the reporting of SAEs (and in particular deaths) involving his/her subjects to the IRB/IEC that approved the trial.

In accordance with ICH GCP guidelines, the Sponsor will inform the Investigator of "findings that could adversely affect the safety of subjects, impact the conduct of the trial or alter the IRB/IEC's approval/favorable opinion to continue the trial." In particular and in line with respective regulations, the Sponsor will inform the Investigator of AEs that are both serious and unexpected and are considered to be related to the administered product ("suspected unexpected serious adverse reactions", SUSARs). The Investigator should place copies of Safety reports in the Investigator Site File. National regulations with regards to safety reporting notifications to investigators will be taken into account. When specifically required by regulations and guidelines, the Sponsor will provide appropriate safety reports directly to the concerned lead IRB/IEC and will maintain records of these notifications. When direct reporting by the Sponsor is not clearly defined by national or site specific regulations, the Investigator will be responsible for promptly notifying the concerned

IRB/IEC of any Safety reports provided by the Sponsor and of filing copies of all related correspondence in the Investigator Site File.

9.12 Monitoring of Subjects with Adverse Events

Any AE that occurs during the course of a clinical trial and is considered to be possibly related to the IP must be monitored and followed up by the Investigator until stabilization or until the outcome is known, unless the subject is documented as "lost to follow-up". Reasonable attempts to obtain this information must be made and documented. It is also the responsibility of the Investigator to ensure that any necessary additional therapeutic measures and follow-up procedures are performed. The Sponsor will actively follow-up and collect information on any AE that occurs during the course of a clinical trial, however while this activity will continue for any

serious AEs until stabilization or until the outcome is known, it will be discontinued at the time of database lock for non-serious AEs.

	-	

59 of 89

60 of 89

11 STATISTICAL METHODS

This section outlines the statistical analysis strategy and procedures for the study. Specific details of the primary and key secondary analyses will be provided in the Statistical Analysis Plan (SAP). If, after the study has begun, but prior to the final analysis, important changes are made to the protocol that affect principal features of the primary or key secondary analyses, then the protocol and/or SAP will be amended, as appropriate. Any other changes made to the planned analyses after the protocol and SAP have been finalized, along with an explanation as to when and why they occurred, will be listed in the Clinical Study Report (CSR) for the study. Post hoc exploratory analyses will be clearly identified in the CSR.

11.1 Populations

11.1.1 Efficacy Analysis

The FAS population will serve as the primary population for the analysis of tumor response and other efficacy-related data. Subjects will be excluded for FAS for the following reasons:

- No baseline data
- Failure to receive at least one dose of tipifarnib
- No post-baseline endpoint data subsequent to at least 1 dose of study drug

A supportive analysis using the Per-Protocol population will be performed for the tumor response analysis. The Per-Protocol population excludes subjects due to important deviations from the protocol that may substantially affect the results of the primary analysis, such as not taking at least 80% of the intended dose in cycle 1. The final determination on protocol violations, and thereby the composition of the Per-Protocol population, will be made prior to locking the clinical database and final analysis and will be documented in a separate memorandum.

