- 6. Major surgery, other than diagnostic surgery, within 4 weeks prior to Cycle 1 Day 1, without complete recovery.
- 7. Active, uncontrolled bacterial, viral, or fungal infections, requiring systemic therapy. Known infection with HIV, or an active infection with hepatitis B or hepatitis C.
- 8. Subjects who have exhibited allergic reactions to tipifarnib or structural compounds similar to tipifarnib or to the drug product excipients. This includes hypersensitivity to imidazoles, such as clotrimazole, ketoconazole, miconazole and others in this drug class. Patients with hypersensitivity to these agents will be excluded from enrolment.
- 9. Required use of concomitant medications classified as strong inhibitors or inducers of cytochrome P450 3A4 (CYP3A4, Table 4) or UDP-glucuronosyltransferase (UGT).
- 10. Concomitant disease or condition that could interfere with the conduct of the study, or that would, in the opinion of the Investigator, pose an unacceptable risk to the subject in this study.
- 11. The subject has legal incapacity or limited legal capacity.
- 12. Significantly altered mental status that would limit the understanding or rendering of informed consent and compliance with the requirements of this protocol. Unwillingness or inability to comply with the study protocol for any reason.

STATISTICAL METHODS:

Descriptive statistics are planned for the pre-screening phase. The sample size was determined based on the expected frequency of HRAS mutations in SQ-NSCLC (~2%). In order to identify up to 18 evaluable subjects that could enroll into the treatment phase, approximately 2000 subjects will be enrolled in the pre-screening phase.

Up to 18 evaluable subjects will be enrolled in the treatment phase using a two-stage design (Simon, 1989). Evaluable subjects are those that have HRAS missense mutant status in a tissue

sample, have an available baseline scan, and have received at least one daily administration (2 doses) of tipifarnib. Seven evaluable study subjects will be enrolled for the first stage; the study will be terminated if 0 responses are observed at end of first stage. Otherwise, an additional 11 subjects will be enrolled for the second stage.

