11.2 Endpoints

11.2.1 Efficacy

The efficacy endpoints are listed in section 5. Up to 18 subjects will be enrolled in the treatment phase of this study. The primary endpoint is overall response rate (ORR) at 6 months, which will be compared to historical control via exact binomial test in comparison to historical control ORR 10%. Binary response endpoints will be summarized by counts and percents of subjects. Traditional 90% confidence intervals for TRUE underlying rates will also be computed and reported.

Correlation of responses with biomarkers will be assessed via comparisons of distributions of biomarkers among various categories of the response endpoints, to be defined in the SAP.

Additional categories of response may be defined and assessed based on the observed data during exploratory analyses.

Summary statistics will be provided for other endpoints.

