11.3 Sample Size Determination

No statistical testing is planned for the pre-screening phase. The sample size was determined based on the expected frequency of HRAS mutations in SQ-NSCLC (2%). In order to identify up to 18 evaluable subjects that could enroll into the treatment phase, approximately 2000 subjects will be enrolled in the pre-screening phase.

Up to 18 evaluable subjects will be enrolled in the treatment phase using a two-stage design (Simon, 1989). Seven evaluable study subjects will be enrolled for the first stage; the study will

be terminated if 0 responses are observed at end of first stage. Otherwise, an additional 11 subjects will be enrolled for the second stage.

At the completion of two-stage study, the study is considered as failure if there are 3 or less responses out of 18 evaluable subjects, indicating the true ORR is 10% or less. If there are 4 or more responses, the treatment will be considered of further interest indicating the true ORR is higher than 10%.

For this two-stage study design, a null response rate of 10% and alternative response rate of 30% are assumed. It provides 80% power to detect a difference between 10% and 30% ORR at one-sided significance level of 0.089. Using this design, the probability of terminating the study at the end of first stage is 0.48 if the true ORR is 10% or less while the probability of terminating the study at the study at the end of first stage is 0.13 if the true ORR is 30%.

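### The primary response-rate population (FAS) and the evaluable set behind the Simon rule are defined differently in the visible text, so the reported ORR, exact test and 90% interval can rest on different subjects from the go/no-go decision

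*Combined protocol and SAP*

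**What the plan says.** **Primary efficacy population (Section 11.1.1).** "The FAS population will serve as the primary population for the analysis of tumor response and other efficacy-related data". The listed exclusions are missing baseline data, failure to take a dose, and "No post-baseline endpoint data subsequent to at least 1 dose of study drug".

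**Decision set (Synopsis, Statistical Methods).** "Evaluable subjects are those that have HRAS missense mutant status in a tissue" specimen. The definition adds two further conditions, namely that these subjects "have an available baseline scan, and have received at least one daily administration (2 doses) of tipifarnib". This is the only place where evaluable is defined. Section 11.3 uses the word without repeating the definition and applies the final rule to that set: "the study is considered as failure if there are 3 or less responses out of 18 evaluable subjects". The stage-1 rule likewise counts seven evaluable subjects.

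**Planned reporting (Section 11.2.1).** The ORR is the primary endpoint, "which will be compared to historical control via exact binomial test in comparison to historical control ORR 10" per cent, and "Traditional 90% confidence intervals for TRUE underlying rates will also be computed and reported". No set is named there, so the FAS of Section 11.1.1 governs. The same section says "Up to 18 subjects will be enrolled in the treatment phase of this study", whereas Section 11.3 and the Synopsis say up to 18 evaluable subjects.

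**Related provisions.** Section 9.1 places the first post-baseline tumor assessment at the end of Cycle 2 and requires responses to be confirmed. Under inclusion criterion 4 (Synopsis and Section 6.1.2), a subject enrolled on a blood result needs tissue confirmation to continue treatment by default. The trial chair may approve continuation when blood is clearly positive and tissue does not confirm.

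**The concern.** In a single-arm trial judged against a fixed 10%, the denominator is part of the result. A written rule that removes treated subjects for lack of post-baseline data removes only people who cannot be confirmed responders. Those most likely to be removed are subjects who die, deteriorate, withdraw or start other treatment before the first scan, about 8 weeks in (two 28-day cycles).

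The go/no-go decision carries no such exclusion. The trial could therefore decide on one response rate and report another, with an exact test and interval that do not describe the set on which the design was built.

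The term *endpoint data* is also undefined. PFS is an efficacy endpoint (Section 5.3), so a death or progression before the first scan may or may not keep a subject in the FAS. That choice should not be left until results are known.

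**Working it through.** **1. Reproduce the design on the evaluable set.** Inputs from Section 11.3: 7 subjects in stage 1, stop at 0 responses; 18 in total, success at 4 or more; null 10%, alternative 30%.

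P(success) = sum over x = 1 to 7 of P(x responses in 7) × P(at least 4 − x responses in 11).

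- At 10%: 0.3720 × 0.0896 + 0.1240 × 0.3026 + 0.0230 × 0.6862 + 0.0027 × 1 = 0.0893. The plan states 0.089.
- At 30%: 0.2471 × 0.6873 + 0.3177 × 0.8870 + 0.2269 × 0.9802 + 0.1260 × 1 = 0.800. The plan states 80%.

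In each line, the last term collects 4 to 7 responses in stage 1. Both figures belong to the evaluable count and do not depend on who is in the FAS.

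**2. Compare the two sets.**

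| Criterion | FAS (11.1.1) | Evaluable (Synopsis) |
|---|---|---|
| Post-baseline data | required | not required |
| HRAS status in tissue | not required | required |
| Doses taken | at least 1 | at least 2 |
| Baseline | baseline data, unspecified | baseline scan |

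The first row can only take non-responders out of the FAS. The other three can put subjects into the FAS who are outside the evaluable count: those positive in blood only, those who took one dose, or those with baseline data but no scan.

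**3. Size.** The documents give no rate for any of these groups, so the numbers dropped or added below are assumptions and could be zero. Start from 4 responders among 18 evaluable, the smallest success. Intervals are Clopper-Pearson 90%, an assumed reading of the plan's term *traditional*: lower limit = 5th percentile of Beta(x, n − x + 1), upper limit = 95th percentile of Beta(x + 1, n − x). The p value is the single-stage P(X ≥ x) at 10%. It ignores the interim stop, so it is descriptive and should not be set against 0.089.

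| Assumed change | FAS result | Exact 90% interval | One-sided p |
|---|---|---|---|
| none | 4/18 = 22.2% | 8.0 to 43.9% | 0.098 |
| 1 unassessed dropped | 4/17 = 23.5% | 8.5 to 46.1% | 0.083 |
| 2 unassessed dropped | 4/16 = 25.0% | 9.0 to 48.4% | 0.068 |
| 1 non-responder added | 4/19 = 21.1% | 7.5 to 41.9% | 0.115 |
| 2 non-responders added | 4/20 = 20.0% | 7.1 to 40.1% | 0.133 |
| 1 blood-only responder added | 5/19 = 26.3% | 11.0 to 47.6% | 0.035 |
| 2 blood-only responders added | 6/20 = 30.0% | 14.0 to 50.8% | 0.011 |

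The rows with 19 or 20 subjects assume other treated subjects beyond 18 evaluable. They could not arise if the cap in Section 11.2.1 were read literally as 18 subjects in all. Dropping 2 unassessed subjects and adding 2 non-responders returns 4/18.

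**4. A case where report and decision point apart.** Suppose 3 of 18 evaluable subjects respond: 16.7% (4.7 to 37.7%), a failure under the rule. One further responder positive in blood only makes the FAS 4/19 = 21.1%. The decision is still failure, but the primary population shows four responses.

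**The case against.** **The text may be reconciled elsewhere.** The contents list a Section 7.2 on replacement of subjects, which is not in the supplied text, and Section 11 leaves analysis details to an SAP, of which no separate text is visible. This stands as a limit: the mismatch can be asserted only of the visible sections. It does not remove the point, because Section 11.1.1 already fixes the primary population and its exclusions.

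**Few subjects may be affected.** Section 9.1 has subjects who stop for reasons other than progression continue tumor assessments, and allows a scan at the End of Treatment visit. If *endpoint data* includes PFS events, early deaths and progressions stay in the FAS. Blood-only subjects are kept on treatment only by exception, and a confirmed response after a single dose is remote. All of this stands, and it is why the numbers above are small and may be zero.

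**The evaluable set is itself a modified set.** It needs a second dose and a tissue result that can arrive after treatment starts, so an all-treated primary set would also be defensible. This stands too. The evaluable set is preferred because the stated significance level and power belong to it.

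**Stronger readings that a reader might infer.** One is that the FAS always inflates the ORR. Only the post-baseline exclusion works in one direction; the tissue, dose and baseline differences can lower or raise the rate. Another is that the decision's type I error is inflated. It is not, because the rule is written on evaluable subjects. A third is that the exclusion could lift the lower 90% limit above 10%: with four subjects dropped, 4/14 = 28.6% has a lower limit of 10.4%. Nothing in the documents suggests losses of that size.

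**Conclusion.** The point holds for the visible text: the primary ORR population and the Simon decision set differ on four criteria, and nothing supplied links them. The defect lies in the reported ORR, its exact test and its 90% interval. The go/no-go rule is sound as written.

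From 4/18 = 22.2%, dropping one or two unassessed subjects gives 23.5% or 25.0%. Adding one or two non-responders gives 21.1% or 20.0%. Adding one or two blood-only responders gives 26.3% or 30.0%. These rest on assumed counts, on the exact-interval reading and, for the additions, on treating more than 18 subjects. The net direction cannot be stated in advance. This should be fixed before the final analysis; confidence is moderate, given the unseen Section 7.2 and SAP.

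**What to change.** - In Section 11.1.1, make the Synopsis evaluable set the population for the primary ORR, its exact test, its 90% interval and both Simon decisions, and name that set in Section 11.2.1.
- Delete the exclusion for absent post-baseline endpoint data as far as ORR is concerned. Count evaluable subjects with no post-baseline tumor assessment, including those with early death or clinical progression, as non-responders.
- Report two sensitivity analyses: all treated subjects, including those positive in blood only, and the current FAS with *endpoint data* defined.
- Check that Section 7.2 and any separate SAP agree, so that no evaluable subject leaves the count merely for lack of a later scan.

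The cost is wording only. The sample size, decision thresholds and stated significance level and power do not change. The reported ORR may be slightly lower than under the current exclusion.

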11.1.2 Safety Analysis

The All Subjects as Treated (ASaT) population will be used for the analysis of safety data. The ASaT population consists of all enrolled subjects who receive at least one dose of tipifarnib. At least one laboratory or vital sign measurement obtained subsequent to at least one dose of study drug is required for inclusion in the analysis of a specific safety parameter. To assess change from baseline, a baseline measurement is also required.

11.2 Endpoints

11.2.1 Efficacy

The efficacy endpoints are listed in section 5. Up to 18 subjects will be enrolled in the treatment phase of this study. The primary endpoint is overall response rate (ORR) at 6 months, which will be compared to historical control via exact binomial test in comparison to historical control ORR 10%. Binary response endpoints will be summarized by counts and percents of subjects. Traditional 90% confidence intervals for TRUE underlying rates will also be computed and reported.

Correlation of responses with biomarkers will be assessed via comparisons of distributions of biomarkers among various categories of the response endpoints, to be defined in the SAP.

Additional categories of response may be defined and assessed based on the observed data during exploratory analyses.

Summary statistics will be provided for other endpoints.

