6.1.2 Treatment Phase

For inclusion of a subject in the treatment phase, all of the following inclusion criteria must be fulfilled:

- 1. Subject has a histologically or cytologically confirmed diagnosis of squamous non-small cell lung cancer (SQ-NSCLC) for which there is no curative therapy available.
- Subject has relapsed (progressive disease) or is refractory to one or more prior therapies. In the case of therapy received in the adjuvant or neo-adjuvant setting, relapse must have occurred within 12 months to be considered prior therapy. Subject may have received prior immunotherapy.
- 3. Subject has a tumor that carries a missense HRAS mutation. HRAS status may have been assessed either in primary tumor tissue, recurrent or metastatic disease.
- 4. Subject has consented to provide tumor slides (or tumour tissue blocks) for biomarker evaluation. Before enrolment the site must confirm the availability of the tumor sample. If there is no sample available, the trial chair must be contacted for approval. If enrolment in the treatment portion of the study has taken place based on HRAS mutant status as

assessed using a blood sample, tumor tissue must be sent before starting cycle 2 of treatment, and It will be used in part for confirmation of HRAS mutant tumor status. Confirmation of HRAS mutant status in tumor tissue is required for continuation of treatment. If HRAS mutation is not confirmed in tumor but is clearly positive in blood, the trial chair will be contacted for approval and the treatment could be maintained. All treated subjects will be evaluated for safety.

- 5. Subject has measurable disease according to RECIST v1.1.
- 6. At least 2 weeks since the last systemic therapy regimen prior to enrolment. Subjects must have recovered to NCI CTCAE v. 4.03 < Grade 2 from all acute toxicities (excluding Grade 2 toxicities that are not considered a safety risk by the Sponsor and Investigator) or toxicity must be deemed irreversible by the Investigator.

- 7. At least 2 weeks since last radiotherapy. If radiation was localized to the only site of measurable disease, there must be documentation of disease progression of the irradiated site. Subjects must have recovered from all acute toxicities from radiotherapy. Subjects may be on a daily dose of corticosteroids (≤ 20mg prednisone or equivalent), as part of their management from prior radiotherapy.
- 8. ECOG performance status of 0 or 1.
- 9. Acceptable liver function:

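### The exact binomial test in section 11.2.1 does not match the two-stage rule in 11.3: at exactly 4/18 it reports p = 0.098 against a stated level of 0.089, although the count rule still decides (minor)

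*Combined protocol and SAP*

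**What the plan says.** **Design.** Section 11.3 and the synopsis (Statistical Methods) set a Simon two-stage design in evaluable subjects. Seven are treated first, and the study is to "be terminated if 0 responses are observed at end of first stage". Otherwise 11 more are added, and three or fewer responses in 18 is a failure. "If there are 4 or more responses, the treatment will be considered of further interest indicating the true ORR is higher than 10"%. The rates assumed are 10% and 30%, with 80% power at a one-sided level of 0.089.

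**Analysis.** Section 11.2.1 takes the response rate at 6 months as primary endpoint, "which will be compared to historical control via exact binomial test in comparison to historical control ORR 10"%. It adds: "Traditional 90% confidence intervals for TRUE underlying rates will also be computed and reported". It mentions neither the stages nor the sidedness or level of the test.

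**Population.** Section 11.1.1 states: "The FAS population will serve as the primary population for the analysis of tumor response and other efficacy-related data". One of its reasons for exclusion is "No post-baseline endpoint data subsequent to at least 1 dose of study drug". The synopsis defines the set that the rule counts differently: "Evaluable subjects are those that have HRAS missense mutant status in a tissue" sample, with a baseline scan and one day of dosing. No post-baseline assessment is required. Section 6.1.2 adds a further case: "If HRAS mutation is not confirmed in tumor but is clearly positive in blood, the trial chair will be contacted for approval", and treatment may then go on.

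**The concern.** The decision rule and its operating characteristics belong to one sampling scheme, and the named test, on its natural reading, belongs to another. A single-sample test of 4/18 includes the path of 0/7 followed by at least 4 of 11. The design cannot produce that path, because it stops at 0/7.

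The clash shows at the success boundary. A report that follows the plan as written would call tipifarnib of further interest and print beside it a p-value above the only significance level in the documents. The documents do not say how to read the two together. The denominator is also open, since the set tested (FAS) is not the set counted (evaluable). If this is settled only after 4 responses have been seen, the choice could look driven by the result.

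**Working it through.** **Inputs.** n1 = 7, stop at 0/7, n2 = 11, success at 4 or more of 18, p0 = 0.10, p1 = 0.30 (section 11.3). Exact binomial test against 10% and 90% interval (section 11.2.1).

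**Step 1: reproduce the plan's level and power.** The probability of declaring further interest is the sum over x = 1 to 7 of P(Bin(7,p) = x) × P(Bin(11,p) ≥ 4 − x).

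- p = 0.10: 0.0893 (stated 0.089).
- p = 0.30: 0.8000 (stated 80%).

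A single-stage rule of 4 or more in 18 would give 0.0982 and 0.835. The stated figures are therefore two-stage quantities.

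**Step 2: the named test at 4/18.** P(Bin(18, 0.10) ≥ 4) = 1 − (0.1501 + 0.3002 + 0.2835 + 0.1680) = 0.0982. Section 11.2.1 gives no sidedness. The two-sided value by the minimum-likelihood method is also 0.0982, and doubling gives 0.196, so no version reaches 0.089.

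**Step 3: the gap.** The impossible path has probability 0.9^7 × P(Bin(11, 0.10) ≥ 4) = 0.4783 × 0.01853 = 0.0089, and 0.0982 − 0.0893 = 0.0089. The only early stop is at 0/7, the lowest outcome under any usual ordering, so the two-stage p-value does not depend on the ordering chosen.

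**Step 4: where the reading changes.**

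| Responses of 18 | Count rule | Single-sample p | Two-stage p |
|---|---|---|---|
| 3 | failure | 0.2662 | 0.2234 |
| 4 | further interest | 0.0982 | 0.0893 |
| 5 | further interest | 0.0282 | 0.0269 |

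Only 4/18 is affected. The probability of passing stage 1 and ending at exactly 4 is P(Bin(18,p) = 4) − P(0/7) × P(Bin(11,p) = 4). At p = 0.30 this is 0.1681 − 0.0824 × 0.2201 = 0.150. At p = 0.20 it is 0.192.

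**Step 5: the 90% interval at 4/18 (5% per tail).** Clopper-Pearson gives 8.0% to 43.9%. The two-stage exact interval, with outcomes ordered by total responses, gives 8.2% to 45.0%. Both include 10%. At 5/18 the lower limits are 11.6% and 11.8%, and both exclude it.

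**Step 6: the population, as illustration only.** The size of the FAS is not given, so n = 16 to 20 is an assumption. With 4 responses, the single-sample P(Bin(n, 0.10) ≥ 4) is 0.068, 0.083, 0.098, 0.115 and 0.133 for n = 16, 17, 18, 19 and 20. Dropping one subject without post-baseline data turns 4/18 (22.2%) into 4/17 (23.5%). Adding one non-responder positive only in blood gives 4/19 (21.1%). This movement comes from the denominator, not from the stages, and 0.089 is the level of the 7 + 11 design, so it is no benchmark at other sizes.

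**The case against.** The strongest reply is that nothing turns on the test. Section 11.3 and the synopsis decide by count, and section 11.2.1 gives its test no threshold and no role in the decision. This stands, and it is why the point is minor.

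Second, section 11.2.1 does not say single-sample. A two-stage exact p-value is also a binomial calculation, and section 11 leaves details of the primary analysis to the SAP. This stands in part: the single-sample reading is an inference. But with intervals described as traditional alongside and no word on stages, it is the natural one. A SAP that simply follows 11.2.1 would inherit the mismatch, and nothing in the available text reconciles the two sections.

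Third, the two sections may not count the same responses. Section 11.2.1 sets a 6-month time point, section 11.3 sets none, and section 9.1 uses confirmed best response. That also stands. The comparison of 0.098 with 0.089 assumes the same four responders, and the fix has to cover the definition.

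Two stronger readings are tempting. A reader might infer that the type I error is inflated. It is not: the single-sample p-value is the larger one, and the count rule keeps its 0.0893. A reader might also infer that success really needs 5/18 and that power is lost. That would require the p-value to be held to 0.089 and to override the count rule, which the documents nowhere say.

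**Conclusion.** The point holds as a minor one. The named test and the stated level do not belong to the same design. At 4/18 the reported one-sided p-value would be 0.098 where 0.0893 is consistent with the design, a difference of 0.009 in the conservative direction. The reading against 0.089 changes at that one outcome only, which has probability 15.0% at a true ORR of 30% and 19.2% at 20%. The conclusion of the trial does not change. Moving to a two-stage interval changes no reading either.

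The population mismatch is a related inconsistency in the text. Its numerical effect depends on how many subjects fall between the two sets, which the documents do not give, and it can go in either direction.

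The figures assume 7 + 11 evaluable subjects, a single-sample reading of the named test, and the same response definition in sections 11.2.1 and 11.3.

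**What to change.** 1. **Section 11.2.1:** state that the count rule of section 11.3, applied to the evaluable subjects defined in the synopsis, is the sole primary decision. Replace the single-sample p-value with the two-stage exact p-value in that set. Quote the design level as 0.0893, so that 4/18 is not read against a rounded 0.089.
2. **Section 11.1.1:** make the evaluable set primary for ORR, count subjects without post-baseline data as non-responders, and keep the FAS as supportive. Changing 11.2.1 alone would leave the FAS as the primary population.
3. **Sections 11.2.1, 11.3 and 9.1:** use one response definition, reconciling the 6-month time point, the untimed count and the confirmed best response.
4. **Section 11.2.1:** label the 90% interval descriptive, because it includes 10% at the success boundary by either method.

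The cost is a few sentences in the protocol or SAP and a few lines of code. No extra patients or data are needed. The change should be in place before the responses are analysed.
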